### **11.4. Pharmacokinetic Analyses**

Pharmacokinetic analyses will be performed on the PK-evaluable population, defined as subjects who have received 1 dose of daratumumab and provided at least one postinfusion sample.

All serum concentrations below the lowest quantifiable concentration in a sample or missing data will be labeled as such in the concentration data listings. Concentrations below the lowest

quantifiable concentration in a sample will be treated as zero in the summary statistics. All subjects and samples excluded from the analysis will be clearly documented in the Clinical Study Report.

Descriptive statistics will be used to summarize daratumumab serum concentrations at each sampling timepoint and PK parameters of daratumumab: Cmin and Cmax. Other PK parameters, when available, will also be summarized.

If sufficient data are available, population PK analysis of serum concentration-time data of daratumumab may be performed and the analysis may include data from other studies. If the population PK analysis is conducted, details will be specified in a population PK analysis plan and the results of the analysis will be presented in a separate report.

### **11.5. Immunogenicity Analyses**

The incidence of antibodies to daratumumab will be summarized for all subjects who receive a dose of daratumumab and have appropriate samples for detection of antibodies to daratumumab.

### **11.6. Pharmacokinetic/Pharmacodynamic Analyses**

Pharmacokinetic/pharmacodynamic modeling of the relationship between serum concentrations of daratumumab and change from baseline in QTc interval will be performed. If sufficient data are available, PK/pharmacodynamic modeling will be performed, including exploring the relationship between serum concentrations of daratumumab and endpoints of clinical efficacy and safety. Details and results of the analysis will be presented in a separate report.

### **11.7. Biomarker Analyses**

Biomarker studies are designed to identify markers predictive of response (or resistance) to daratumumab. Analyses will be stratified by clinical covariates or molecular subgroups using the appropriate statistical methods (eg, parametric or non-parametric, univariate or multivariate, analysis of variance [ANOVA], or survival analysis, depending on the endpoint). Correlation of baseline expression levels or changes in expression levels with response to time-to-event endpoints will identify responsive (or resistant) subgroups in addition to genes and pathways attenuated following treatment with daratumumab.

Any pharmacodynamic measures will be listed, tabulated, and where appropriate, plotted. Subjects may be grouped by dose schedule or clinical response. As this is an open-label study without a control treatment, statistical analyses will be done to aid in the understanding of the results.

Results of biomarker and pharmacodynamic analyses may be presented in a separate report. Planned analyses are based on the availability of clinically valid assays and may be deferred if emerging study data show no likelihood of providing useful scientific information.

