|  | Notes  | within 28 days before randomization | 8-week cycles   | at 28 ± 7 days after last dose     |           |
| HBV DNA test   | For subjects with serologic evidence of resolved HBV infection (ie, positive Anti-HBs or positive Anti-HBc) at Screening, HBV DNA testing by PCR must be performed locally. Refer to Section 9.5.2.  |                                     | Prior to re-initiation, Q12W during treatment, at the End of Treatment Visit, and Q12W for up to 6 months after the last dose of study treatment  |                                    |           |
| Serum chemistry  |  | X                                   | Please see Table 3 for details.   |                                    |           |
| Whole blood  | Plasma and PBMC biomarker assessments  |                                     | C1D1, C4D1  | X                                  |           |
| Whole blood  | Immunophenotyping  |                                     | C1D1, C2D1, C4D1, C8D1  | X                                  |           |
| Daratumumab PK   | During treatment phase, 1 sample to be collected before start (window -2 hrs) and 1 sample immediately after end (window +2 hrs) of dara infusion. For subjects in QTc substudy, see Table 2 for collection on C1D1 and C1Wk8. Samples to be sent to central laboratory.       |                                     | Arm A: C1D1, C1Wk8 (day of Dose #8), C2D1, C3D1, C4D1, C6D1, C8D1
Arm B: C1D1, C1Wk8, C2D1, C3D1, C4D1, C6D1
Arm C: C1D1, C1Wk8   | 4wks and 8wks after last dara dose |           |
| Daratumumab immunogenicity   | No additional sample needed for planned timepoints; will be taken from PK sample. All planned treatment phase timepoints are pre-dose only.  |                                     | Arm A: C1D1, C2D1, C4D1, C6D1
Arm B: C1D1, C2D1, C4D1, C6D1
Arm C: C1D1, C1Wk8
If an infusion reaction occurs, obtain unscheduled blood sample as soon as possible.                                    | 4wks and 8wks after last dara dose |           |
| Disease Evaluations: Subjects in Arm C will continue disease assessments per schedule below after completion of treatment in Cycle 1. For all subjects, every effort should be made to conduct disease evaluations as per schedule (window ±7 days). Refer to Section 9.2 for details |  |                                     |   |                                    |           |

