|                                      |  | within 28 days before randomization  | 8-week cycles   | at 28 ± 7 days after last dose |           |
| Hemoglobin, creatinine               | At screening and during treatment, these tests are included in the local hematology and clinical chemistry tests.  |  | After completion of study treatment, obtain with disease assessments until PD.  |                                |           |
| Bone marrow aspirate/biopsy          | Acceptable for screening if performed as part of SOC within 56 days before randomization. A fresh aspirate is requested for assessment of genetic modifications, establishment of the MM clone for MRD evaluation, and immunophenotyping (all central lab). If fresh aspirate is not collected, then unstained, non-decalcified diagnostic tissue must be collected (see Section 9.2.1.7 for details). For disease confirmation, archival tissue may be used (may be local lab). | X  | At suspected CR and at 12 months and 18 months after first dose for subjects who maintain CR. Only fresh aspirate is needed for biomarker assessment. Core biopsy or aspirate is needed for clinical evaluation of CR/sCR. An additional aspirate, if feasible, will be taken within 2 months of PD diagnosis.  |                                |           |
| Blood sample for CMMCs               | As of Amendment 4, these samples will no longer be collected.  | X  | At suspected CR, and at 12 months and 18 months after first dose for subjects who maintain CR   | X                              |           |
| Skeletal radiography, or low-dose CT | Screening assessment may be performed within 56 days before randomization  | X  | Use same methodology during study as used at screening: Skeletal radiography or low-dose CT q12 months, and at biochemical progression (eg, increase in SPEP >25%) or at suspected PD. For subjects with (1) negative MRI results at baseline, (2) M-protein increase ≤25%, and (3) no other signs of clinical progression, only an MRI needs to be performed. For these subjects, low-dose whole body CT or skeletal survey does not need to be repeated unless focal lesions have been identified by MRI. |                                |           |

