**Table 6: Bone Marrow Testing**

|                            | Local Testing   | Central Testing   |
|----------------------------|---|---|
| Screening           | Disease characterization (morphology and either immunohistochemistry, immunofluorescence, or flow cytometry). Cytogenetics by conventional karyotype or FISH.   | MRD and molecular subtyping: a portion of bone marrow aspirates collected at screening will be sent to a central laboratory.
If a fresh bone marrow aspirate will not be performed at screening because a sample is available within 56 days prior to randomization, then unstained, non-decalcified diagnostic tissue [bone marrow aspirate slides, touch prep from biopsy (rolled biopsy) slides, or clot specimen slides] must be collected for MRD assessment. |
| CR, sCR             | For response confirmation, additional bone marrow aspirates or biopsies (or both) will be performed locally to confirm sCR or CR.
For sCR: immunohistochemistry, immunofluorescence (requires kappa/lambda ratio from analysis of $\geq 100$ cells) or 2- to 4-color flow cytometry. | MRD: a portion of bone marrow aspirates collected during these timepoints will be sent to a central laboratory.   |
| Maintained CR, sCR  | Not applicable.   | MRD: For subjects who maintain CR, an additional bone marrow aspirate will be obtained 12 and 18 months (+/-1 month) after first dose and sent to central laboratory.   |
| Disease Progression | Not applicable.   | If feasible, a bone marrow aspirate may be collected from subjects at disease progression to evaluate mechanisms of daratumumab resistance.   |

CR=complete response; FFPE=formalin-fixed paraffin embedded; FISH=fluorescence in situ hybridization; MRD=minimal residual disease; sCR=stringent complete response

A portion of the bone marrow aspirate at baseline and at disease progression when feasible will be utilized for DNA/RNA sequencing to characterize subjects (t(4;14), del17p, t(14;16), UAMS70, etc) and to evaluate potential mechanisms of resistance (CD38 mutations, expression of CD38 and CD59).

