#### 9.4. Biomarkers

As of Amendment 5, samples for the evaluation of biomarkers described below will not be collected. Refer to [Attachment 4](#) for a description of study procedures for subjects who continue in the Treatment Extension Phase or who have discontinued treatment but remain in Follow-up.

Biomarker assessments will focus on 4 main objectives including evaluating the ability of daratumumab to reduce MRD in SMM subjects who achieve a complete response, to determine the clinical benefit (ORR, PFS, and OS) of daratumumab in subjects with genetic modifications, to evaluate the immunophenotype of SMM patients for potential immune cell contributions to daratumumab response, and to evaluate the contribution of CMMCs to progression of disease. All biomarker assessments will be performed centrally.

Bone marrow aspirates will be collected at screening and following treatment as outlined in the Time and Events Schedule. Baseline bone marrow aspirates will be subjected to DNA sequencing in order to establish the myeloma clone for MRD monitoring. A fresh bone marrow aspirate at Screening is required if at all possible, for MRD assessment. If bone marrow aspirate is not available, unstained, non-decalcified diagnostic tissue [bone marrow aspirate slides, touch prep from biopsy (rolled biopsy) slides, or clot specimen slides] must be supplied for MRD assessment instead. For subjects who achieve a CR or sCR, additional bone marrow aspirate will be utilized for assessment of MRD by next-generation sequencing (NGS) of immunoglobulin heavy and light chains (Vij 2014). For subjects who maintain a CR, MRD will also be assessed at 12 and 18 months after first dose in bone marrow aspirate. If this methodology is unavailable, or determined to be scientifically inferior, then alternative methods for MRD assessment may be utilized. In cases where daratumumab is suspected of interfering with serum IFE and preventing clinical CR response calls, subjects with VGPR may also be evaluated for MRD by NGS.

In addition to MRD evaluations, bone marrow aspirates will be utilized for whole exome DNA/RNA sequencing in subjects with genetic modifications (t(4;14), t(14;16), del17p, UAMS-70, etc) and to monitor for potential predictive biomarkers of response and/or resistance, including changes in CD38 and CD59 expression. In addition, changes in expression patterns of genes associated with ADCC, CDC, or other mechanisms of action of daratumumab may be evaluated.

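### Section 11.7: changes in marrow expression cannot act as predictors of response or progression, because post-baseline marrow sampling is largely triggered by those same outcomes

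*Protocol*

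**What the plan says.** Protocol Section 11.7 sets out the biomarker analysis: "Correlation of baseline expression levels or changes in expression levels with response to time-to-event endpoints will identify responsive (or resistant) subgroups". I read this as covering both response and time-to-event endpoints. It offers two predictors, baseline level and change in level, and does not name the tissue.

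Section 9.4 places expression change in the marrow. Aspirates are to be used "to monitor for potential predictive biomarkers of response and/or resistance, including changes in CD38 and CD59 expression", and changes in the expression of genes linked to the drug's mechanisms may also be examined.

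The marrow schedule is in Table 1. After screening, samples are due "At suspected CR and at 12 months and 18 months after first dose for subjects who maintain CR". For progressors, "An additional aspirate, if feasible, will be taken within 2 months of PD diagnosis". The text under Table 6 (Section 9.2.1.7) is narrower still: "A portion of the bone marrow aspirate at baseline and at disease progression when feasible will be utilized for DNA/RNA sequencing to characterize subjects". Table 6 itself assigns the central samples at CR and maintained CR to MRD, and the aspirate at progression to the study of resistance.

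Blood is handled differently. Table 1 schedules immunophenotyping at "C1D1, C2D1, C4D1, C8D1" and at end of treatment, and plasma/PBMC markers at C1D1, C4D1 and end of treatment. Section 9.4 uses these for response and resistance markers too.

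The SAP has no biomarker section.

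**The concern.** A predictor has to be measurable before the outcome, and in subjects who go on to have it as well as in those who do not. A change in marrow expression meets neither condition. The second sample is taken because CR is suspected or maintained, or because PD has been diagnosed. For a change read at PD, the interval between the two samples is close to the time to PD itself, so any marker that moves with time on study will track PFS whether or not it predicts anything.

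Subjects who remain in stable disease or PR contribute no change value, so a responder versus non-responder comparison of marrow change has no proper non-responder group; its only members are those who progressed.

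What is at stake is modest but real. Finding predictive markers is a stated exploratory objective, and 11.7 says the analysis will identify subgroups. A spurious resistance marker could be carried into later work.

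**Working it through.** The documents give no figure for this analysis, so there is nothing to reproduce. The argument rests on the schedule; the arithmetic only shows its scale.

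**1. What triggers each sample**

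| Sample | Timing | Depends on outcome? |
|---|---|---|
| Marrow | Screening | No |
| Marrow | Suspected CR | Yes, response |
| Marrow | Months 12 and 18 | Yes, only if CR is maintained |
| Marrow | Within 2 months of PD, if feasible | Yes, progression |
| Marrow evaluated for MRD in some VGPR subjects (Section 9.4) | Suspected drug interference with immunofixation | Yes, response |
| Blood | C1D1, C2D1, C4D1, C8D1 | No, fixed visit |

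No row gives a post-baseline marrow to a subject in stable disease or PR who does not progress.

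**2. How many subjects would have a marrow change value**

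Inputs from Protocol Section 11.2: n = 120; CR rate 15% or 35%; PD/death rate 0.185 or 0.346 per patient-year. Assumption: 1.0 to 2.0 years of follow-up, since the second cutoff is 12 months after the last randomization and accrual time is not stated.

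- CR-triggered marrow: 120 × 0.15 = 18 to 120 × 0.35 = 42.
- P(event) = 1 − exp(−rate × years). Lowest: 1 − exp(−0.185 × 1) = 0.169, or 20 subjects. Highest: 1 − exp(−0.346 × 2) = 0.499, or 60 subjects. These are upper bounds for PD marrow, because deaths yield none and collection is only if feasible.
- No post-baseline marrow, CR and PD independent: (1 − 0.15)(1 − 0.169) = 0.706, or 85 subjects, down to (1 − 0.35)(1 − 0.499) = 0.325, or 39.
- No post-baseline marrow, PD only in non-CR subjects: 1 − 0.15 − 0.169 = 0.681, or 82, down to 1 − 0.35 − 0.499 = 0.151, or 18.

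For sequencing-based expression only the PD sample counts, so at least 120 − 60 = 60 to 120 − 20 = 100 subjects would lack a value. Section 11.7 sets no analysis date. With follow-up uniform on 4 to 5 years, the event-free share is [exp(−4r) − exp(−5r)]/r = 0.436 (r = 0.185) or 0.212 (r = 0.346), so 52 or 25 subjects. The gap shrinks with time; the circularity does not.

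**3. Illustration of the bias**

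Let a marker have no predictive value and let change at PD = b × (months to PD) + N(0,1). Its correlation with time to PD is b·SD(T)/√(b²Var(T) + 1), which is zero only if b = 0. In simulated trials of 120 subjects (12-month accrual assumed, about 29 to 48 with events), a two-sided 5% Pearson test rejected as follows:

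| Drift b, SD per month | Rate 0.185 | Rate 0.346 |
|---|---|---|
| 0 | about 5% | about 5% |
| 0.01 | 7% | 7% |
| 0.05 | about 30% | 47% |
| 0.10 | 80% | 95% |

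At b = 0.02 the rate was 9% to 12%. A second simulation (4,000 runs, CR 35%, rate 0.185, 1.5 years) compared change in CR-sampled with change in PD-sampled subjects, where the level depends only on disease state at sampling. It rejected in 5%, 41%, 94% and 100% of runs for state differences of 0, 0.5, 1 and 2 SD. Baseline and fixed-time markers stayed at about 5% to 6%.

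**4. Blood at a fixed visit**

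The share with PD or death by the visit is 1 − exp(−rate × days/365.25): 3% to 5% by C2D1 (56 days), 8% to 15% by C4D1 (168 days), 18% to 31% by C8D1 (392 days). An early visit loses few subjects.

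**The case against.** The strongest reply is that the sentence in 11.7 never mentions marrow, and half of it concerns baseline levels. A reader might infer that the whole biomarker plan is unable to identify subgroups. The documents do not support that: baseline expression is collected before treatment, and the cycle-based blood draws do not wait for an outcome. That part of the objection stands in full.

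A reader might also infer that blood changes analysed from randomization carry immortal-time bias. For relative effects this largely fails. If every analysed subject has a value at the same visit, all share the same event-free lead-in, and shifting the time origin by a constant leaves the Cox risk sets, and so the hazard ratio, unchanged. Only absolute survival curves and the population described are affected.

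It can further be said that 11.7 allows survival methods chosen to suit the endpoint, that Table 6 already gives PD marrow a resistance purpose, and that the analyses may be deferred. These points limit the weight. They do not repair the marrow-change component: neither a landmark nor a time-dependent covariate helps when the value does not exist until the event has happened, and neither document confines marrow change to descriptive use.

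**Conclusion.** The concern holds for one component: correlating changes in marrow expression with response or time-to-event outcomes. Followed as written, that analysis conditions the predictor on the outcome and leaves out subjects who reach neither CR nor PD. The conclusion rests on Tables 1 and 6 and needs no numerical assumption.

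The size does depend on assumptions. It would be tempting to quote a single false-positive rate or missing fraction. The documents fix no drift, no test and no analysis date, so the rates are illustrations only: near 5% with no drift and rising as drift grows. The missing share likewise depends on the follow-up chosen.

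Severity is minor. The objective is exploratory, the analyses can be deferred or dropped, and no primary or secondary endpoint relies on them.

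**What to change.** Amend Section 11.7, or the biomarker analysis plan if one is written:

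- Limit analyses meant to predict response, PFS or OS to baseline markers and to blood changes at one fixed early visit (for example C4D1). Include only subjects event-free at that visit and, for response, not yet responding.
- Do not treat the end-of-treatment blood draw as a fixed visit, because PD ends treatment and so can set its date. State which visit applies in Arm C, which is treated in Cycle 1 only.
- Report marrow changes at CR and at PD as paired descriptive data, for instance on mechanisms of resistance as Table 6 intends, and not as correlates of response or time-to-event outcomes.

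The cost is wording. No new samples are needed, which matters because biomarker collection ended with Amendment 5. The one loss is that early progressors, and for response early responders, drop out of the fixed-visit blood analysis; they remain in the baseline-marker analysis.

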## 11.8. Safety Analyses

### Adverse Events

The verbatim terms used in the eCRF by investigators to identify AEs will be coded using the Medical Dictionary for Regulatory Activities (MedDRA). The severity assessment for an AE or SAE should be completed using the NCI-CTCAE Version 4. All reported AEs with onset during the treatment phase (ie, treatment-emergent AEs, and AEs that have worsened since baseline) will be included in the analysis. For each AE, the percentage of subjects who experience at least 1 occurrence of the given event will be summarized by treatment group.

Summaries, listings, datasets, or subject narratives may be provided, as appropriate, for those subjects who die, who discontinue treatment due to an AE, or who experience a severe or a serious AE.

### Clinical Laboratory Tests

Laboratory data will be summarized by type of laboratory test. Reference ranges and markedly abnormal results (specified in the Statistical Analysis Plan) will be used in the summary of laboratory data. Descriptive statistics will be calculated for each laboratory analyte at baseline and for observed values and changes from baseline at each scheduled time point. Changes from baseline results will be presented in pre- versus post treatment cross-tabulations (with classes for below, within, and above normal ranges). Frequency tabulations of the abnormalities will be made. A listing of subjects with any laboratory results outside the reference ranges will be provided. A listing of subjects with any markedly abnormal laboratory results will also be provided.

Parameters with predefined NCI-CTCAE toxicity grades will be summarized. Change from baseline to the worst toxicity grade experienced by the subject during the study will be provided as shift tables. Worst toxicity grade during treatment will be presented, according to NCI-CTCAE (version 4). Clinically relevant changes (ie, causing a treatment intervention and/or need for concomitant therapy) will be also recorded on the AE eCRF. All other lab abnormalities need not be recorded as AEs.

### Vital Signs

Descriptive statistics of temperature and blood pressure (systolic and diastolic) values and changes from baseline will be summarized. The percentage of subjects with values beyond clinically important limits will be summarized.

### ECG Analysis

QT interval corrected for heart rate using Fridericia's (QTcF) and Bazett's (QTcB) formulae will be calculated. Descriptive statistics of QTc intervals and changes from baseline will be summarized at each scheduled timepoint. A mixed effects analysis of variance (ANOVA) model will be fit with QTc as the dependent variable, scheduled timepoint of measurement as the fixed effect, and subject as a random effect. Using the means and intrasubject variance obtained from this model, 2 sided 90% confidence intervals will be calculated for the difference in the mean QTc

from baseline at each scheduled timepoint. An effect on QTc will be ruled out if the upper bound of the 90% confidence interval for the difference in means between the postbaseline QTc (at each timepoint) and baseline QTc is less than 20 milliseconds.

The proportion of subjects with a post-dose QTc interval >450 milliseconds and >480 milliseconds will be summarized, as will the proportion of subjects with QTc interval increases from baseline >30 milliseconds or >60 milliseconds. A listing of subjects with a QTc interval >500 milliseconds will also be provided.

The proportion of subjects with post-dose PR interval >200 milliseconds, QRS >110 milliseconds, and heart rate >100 bpm and <50 bpm will be reported. The proportion of subjects with ST segment and T and U wave abnormalities will be reported.

All important abnormalities in ECG waveform that are changes from the baseline readings will be reported (eg, changes in T-wave morphology or the occurrence of U waves).

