#### **QTc Evaluation Substudy**

For subjects participating in the QTc evaluation substudy, the QTc endpoint will be the change in QTc interval (at each measured timepoint) from time matched baseline, where baseline is the QTc measurement before any administration of daratumumab.

For the first 30 subjects eligible for the QTc substudy at sites participating in the QTc evaluation substudy, 12-lead ECGs will be obtained at the following timepoints (see Time and Events Schedule for allowable windows):

- Screening (one day from the range Day -14 to Day -1): 1:00 PM, 2:00 PM, 3:00 PM, 4:00 PM, 5:00 PM
- Cycle 1, Dose 1: pre-dose and after the end of infusion
- Cycle 1, Dose 8: pre-dose, after the end of infusion, and 1 hour after the end of infusion

ECGs must be performed with the subject in the same comfortable supine resting position for at least 10 minutes before the ECG tracings. Pre-dose ECGs will be obtained in the time period following administration of preinfusion medications but before the daratumumab infusion. The 12 lead ECGs will be done in triplicate (three 10 second digital ECGs within 5 minutes). It is important to note that the actual test time should be consistent with a timepoint for both the screening and on-study ECGs, to minimize variability in the results obtained. Similarly, for subjects participating in ECG data collection, daratumumab infusions should be administered beginning at approximately the same time of day for Doses 1 and 8 in Cycle 1.

Vital signs, ECGs, and PK samples must be collected according to the timepoints and windows specified in [Table 2](#). On days when triplicate ECGs are scheduled, pre-dose assessments should be performed in the following order:

1. Administer preinfusion medications.
2. Measure vital signs.
3. Obtain triplicate ECGs.
4. Draw blood samples for PK.
5. Administer daratumumab infusion.

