### 11.2. Sample Size Determination

Two hypotheses will be tested:

1.  $H_0$ : CR rate  $\leq 15\%$   
 $H_a$ : CR rate  $\geq 35\%$
2.  $H_0$ : PD/death rate  $\geq 0.346/\text{patient-year}$  (median PFS  $< 24$  months)  
 $H_a$ : PD/death rate  $\leq 0.185/\text{patient-year}$  (median PFS  $> 45$  months)

This study will enroll 120 subjects (40/arm) in total. With 40 subjects per arm, each arm will have:

- 90% power to show that the true CR rate is 35% at a one-sided level of 0.05
- 80% power to show that the true PD/death rate is 0.185/patient year at a one-sided level of 0.1

If two or more treatment schedules are deemed to be effective, with 40 subjects per arm this study would have:

- 85% probability of identifying the arm with the higher CR
- 80% probability of identifying the arm with the lower PD/death rate

For the QTc substudy, assuming that the intrasubject standard deviation for change from baseline in QTc ( $\Delta\text{QTc}$ ) is 20 milliseconds and that the true difference in means is 5 milliseconds, a sample size of 25 evaluable subjects (completers) will have 80% power to show that the upper limit of the two-sided 90% confidence interval (1 sided upper 95% confidence interval) for the difference in mean QTc ( $\Delta\text{QTc}$ ) at each timepoint and baseline will be less than 20 milliseconds. To ensure 25 subjects are evaluable, the QTc substudy will enroll approximately 30 subjects.

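### The QTc 90% intervals in protocol 11.8 all rest on one pooled intrasubject variance; the three-day, time-matched ECG schedule makes that doubtful, so the 20 ms rule can be miscalibrated in either direction

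*Protocol*

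**What the plan says.** Protocol 11.8 (ECG Analysis) fits a mixed-effects ANOVA to QTc with "scheduled timepoint of measurement as the fixed effect, and subject as a random effect. Using the means and intrasubject variance obtained from this model", and forms a two-sided 90% interval for the mean difference from baseline at each scheduled timepoint. An effect is ruled out if the upper bound for the difference between post-baseline QTc, at each timepoint, and "baseline QTc is less than 20 milliseconds".

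Protocol 9.5.1 (QTc Evaluation Substudy) states that "the QTc endpoint will be the change in QTc interval (at each measured timepoint) from time matched baseline", with baseline taken before any daratumumab. The ECGs are:

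- five hourly readings, 1 to 5 PM, at "Screening (one day from the range Day -14 to Day -1");
- two at Cycle 1 Dose 1 (pre-dose, end of infusion);
- three at Cycle 1 Dose 8 (pre-dose, end of infusion, one hour later), which Table 3 places on Day 50.

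The mean of each triplicate is the analysed value.

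Protocol 11.2 sizes the substudy by "assuming that the intrasubject standard deviation for change from baseline in QTc" "is 20 milliseconds and that the true difference in means is 5 milliseconds". That gives 25 completers and 80% power on the "upper limit of the two-sided 90% confidence interval (1 sided upper 95% confidence interval").

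The SAP repeats the sample size (1.4), assigns QTc analysis and reporting to an external vendor (1) and adds nothing on the QTc model (6.6). Neither document has a subject-by-day term, an unstructured covariance or a variance of paired changes.

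**The concern.** With subject as the only random effect, the model gives every pair of a subject's readings the same correlation. Readings on one day share whatever is particular to that day. A change from the screening day to a dosing day also carries day-to-day variation. Readings at the same hour on different days may share a clock-time pattern, which time-matching removes from the change but which stays in the pooled residual. One variance cannot represent all these contrasts.

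Section 11.8 also does not say which reading is the baseline. The screening timepoints are clock times and the dosing-day timepoints are relative to the infusion, so a contrast of timepoint means does not by itself match each subject's hour.

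At stake is a stated secondary objective, the effect on the QT interval. It is decided by whether the upper bound lies below 20 ms, so the width of the interval matters directly.

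**Working it through.** **Inputs.** From the documents: n = 25, margin 20 ms, true difference 5 ms, SD 20 ms, one-sided 5% (11.2); timepoints 5 + 2 + 3 on three days (9.5.1). Not in the documents, so assumed: the split of within-subject variance into a subject-by-day part *d*, a subject-by-clock-time part *c* and a remainder *w*, with w + d + c = 1.

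**1. The plan's own figure.** The distance to the margin is 20 − 5 = 15 ms.

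- If 20 ms is the SD of the change: SE = 20/√25 = 4, and power = Φ(15/4 − 1.645) = Φ(2.105) = 98.2% (97.7% with t, 24 df).
- If 20 ms is the SD of one reading: SE = 20√(2/25) = 5.66, and power = Φ(2.652 − 1.645) = Φ(1.007) = 84.3% (82.4% with t, 24 df; 24 subjects then reach 80%).

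The stated 80% fits only the second reading, which is also the form of the ANOVA interval, so it is used below. The wording in 11.2 mixes the two.

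**2. Day-to-day variation only (c = 0).** Ten timepoints make 45 pairs. Same-day pairs number 10 + 1 + 3 = 14, so 31 are on different days, and 31/45 = 0.689. The residual variance estimates w + 0.689d. A between-day change of single readings needs w + d. With *s* the day share:

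SE ratio (model/correct) = √((1 − s) + 0.689s); one-sided error = Φ(−1.645 × ratio).

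| Day share s | SE ratio | Error at one timepoint | Coverage of 90% CI | Error, simulated (n = 25) |
|---|---|---|---|---|
| 0 | 1.000 | 5.0% | 90.0% | 4.9% |
| 25% | 0.960 | 5.7% | 88.6% | 6.0% |
| 50% | 0.919 | 6.5% | 86.9% | 6.6% |
| 75% | 0.876 | 7.5% | 85.0% | 7.3% |
| 100% | 0.830 | 8.6% | 82.8% | 8.8% |

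If only one screening reading enters the model (1 + 2 + 3), the fraction is 11/15 = 0.733 and the worst case is a ratio of 0.856 with 8.0% error.

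**3. Adding a clock-time component.** Assume that each post-infusion reading shares an hour with one screening reading and that the two pre-dose readings share an hour of their own. Then 4 of the 45 pairs share a clock time and 41/45 = 0.911 do not. The residual estimates w + 0.689d + 0.911c, while a matched between-day change needs w + d.

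- d = 0.25, c = 0.25, w = 0.50: 0.900 against 0.75, ratio √(0.900/0.75) = 1.095. The interval is too wide, with error Φ(−1.80) = 3.6% (about 4% by simulation).
- d = 0.25, c = 0.10, w = 0.65: 0.913 against 0.90, ratio 1.007.
- d = 0.50, c = 0.10, w = 0.40: 0.836 against 0.90, ratio 0.964.
- d = 0.50, c = 0.25, w = 0.25: 0.822 against 0.75, ratio 1.047.

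**4. Dose 1 pre-dose ECG as baseline.** It too precedes any drug. The Dose 1 post-infusion change is then same-day and, with c = 0, needs only w. The ratio is √(0.922/0.75) = 1.11 at a 25% day share and √(0.844/0.50) = 1.30 at 50%, so the interval is too wide.

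**5. Effect on the bound.** The model half-width is 1.645 × 5.66 = 9.3 ms.

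- True change 5 ms: expected bound 14.3 ms from the model, and 5 + 9.3/0.830 = 16.2 ms at the worst row of the table. Both are below 20.
- True change 10 ms (protocol 3.2 reports a pre-to-post QTcF increase of about that size in an earlier study, not time-matched): 19.3 ms from the model; 19.7/20.1/20.6 ms corrected at day shares of 25/50/75%; 10 + 9.3/1.095 = 18.5 ms under the 25% day, 25% clock case.
- If 20 ms is instead the SD of the change, the half-width is about 6.6 ms and the model bound at 10 ms is 16.6 ms. Even 10 + 6.6/0.830 = 18.0 ms does not reach 20.

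**6. All timepoints together.** In the simulations of step 2, with every dosing-day timepoint at a true 20 ms, all passed in 0.3/0.6/0.9% of runs at day shares of 25/50/75%, against 0.2% with no day effect.

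**The case against.** The strongest reply is that the documents fix neither the size nor the sign of the error. They give no day-to-day QTc variance; if it is zero and there is no clock-time component, the planned interval is correct. Protocol 9.5.1 asks for consistent test times, and matching can make the planned interval conservative. This stands, and it limits the point to possible miscalibration in either direction.

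Second, an effect is ruled out only if every timepoint passes. This also stands: the rates in step 2 are per timepoint and approach the error of the whole rule only if one timepoint sits at 20 ms and the others well below.

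Third, with complete data the difference of timepoint means is the mean change. That is right for a fixed pair of timepoints; the estimate is then not in question, only its standard error.

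Fourth, protocol section 11 calls itself a general description and the vendor's plan is not among the documents, so a suitable covariance may be set there. That is possible, but 11.8 names the variance to be used and nothing visible changes it.

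Fifth, Table 2 records the substudy as complete as of Amendment 4, so replacing the primary method now would be post hoc. This affects how the fix is presented. It does not make the stated method valid.

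A reader might also infer a larger error by averaging the five screening readings. The model would then use 1.2(w + 0.689d) where 1.2w + 2d is needed, making the interval 11/20/28% too narrow with 7.2/9.5/12.0% error at day shares of 25/50/75%. The documents do not support this, because 9.5.1 specifies a time-matched baseline.

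**Conclusion.** The point holds as a question of calibration. Section 11.8 uses one pooled variance for contrasts that the schedule makes unlikely to share one, and neither document corrects this.

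A reader might infer that the interval is always too narrow, or that the QT conclusion carries a 6 to 8% false rule-out rate. Neither follows. The interval is too narrow under day-to-day variation without a clock-time component, and too wide with a sizeable clock-time component or with a same-day baseline. The day and clock shares are assumptions throughout, and the clock case also rests on an assumed assignment of readings to hours.

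The consequence is modest. At the planned 5 ms the bound stays below 20 ms in every case shown. At 10 ms, with 20 ms as the per-reading SD, the correction can move the expected bound across 20 ms at assumed day shares of 50% and above. The issue merits correction because this interval alone decides the objective and the remedy needs no new data.

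**What to change.** In 11.8 and the vendor's analysis plan:

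- State which reading is the time-matched baseline for each post-baseline timepoint, including whether the Dose 1 pre-dose ECG ever serves.
- Calculate each subject's change at each post-baseline timepoint. Take the two-sided 90% interval from the SD of those changes (t, n − 1 df), or from a repeated-measures model on the change with unstructured covariance.
- Because the substudy is complete, report this at least as a sensitivity analysis beside the planned ANOVA, labelled as added afterwards.
- Say in 11.2 whether 20 ms is the SD of the change or of a single reading.

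The 20 ms margin and the sample size stay as they are. In simulation the paired-change interval held 4.5 to 5.8% error in every case tried. The cost is an interval about 3% wider if readings are in fact equally correlated: with an SD of change of 20 ms and n = 25, a half-width of 6.8 ms (t, 24 df) against 6.6 ms (t, 24 × 9 = 216 df).
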